7.1 Study Procedures

7.1.1 Screening, Enrollment, and/or Randomization

Informed consent must be obtained before completing any screening procedure or discontinuation of standard therapy for any disallowed therapy. After the subject has signed the ICF, the site will screen the subject to assess eligibility for participation. The screening window is up to 40 days.

All screening evaluations must be completed and reviewed to confirm that potential subjects meet all eligibility criteria. The investigator will maintain a screening log to record details of all subjects screened and to confirm eligibility or record reasons for screening failure, see Section 4.3 as applicable.

If a subject has not met all eligibility criteria at the end of the screening period, the subject will be registered as a screen failure. Screen failed subjects may be eligible for re-screening 3 times.

Once the subject is registered as rescreened, a new 40-day screening window will begin. Subjects will retain the same unique identification number assigned at the original screening. If the rescreening period begins more than 40 days after the original signing of the ICF, all screening procedures, including informed consent, must be repeated as well.

Laboratory assessments used to determine subject eligibility may be repeated once for confirmation, allowing for up to a total of two assessments during the 40-day screening period, if necessary, before the subject is considered a screen failure. If any assessments are repeated

during the screening period, the value that is closest to the enrollment date will apply for the determination of eligibility.

If the initial BP measurement is elevated, the assessment may be repeated again at least 15 minutes later and the lower of the 2 readings may be used for Screening.

Subjects will be assigned a randomization number based in sequential order in which they qualified to be randomized, in accordance with the randomization schedule. Subjects are considered randomized once a unique subject randomization number has been assigned.

The point of enrollment occurs at the time of subject randomization number allocation. The enrollment date is the same as the randomization date.

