7.6 Safety and Tolerability Assessments

7.6.1 Treatment-Emergent Adverse Events and Serious Treatment-Emergent Adverse Events: Time Period and Frequency for Collecting and Reporting Safety Event Information

TEAE definitions, assignment of severity and causality, and procedures for reporting serious TEAEs are detailed in [Appendix 1](#).

The condition of each subject will be monitored from the time of signing the ICF to EOS visit. Subjects will be observed for any signs or symptoms and asked about their condition by open questioning, such as "How have you been feeling since you were last asked?", at least once each day while resident at the study site and at each study visit. Subjects will also be encouraged to spontaneously report TEAEs occurring at any other time during the study.

Treatment-emergent adverse events

The TEAE grading scale to be used in this study is described in "Assessment of Severity" in [Appendix 1](#).

The Investigator is responsible for ensuring that all non-serious TEAEs observed by the Investigator or reported by the subject (whether reported by the subject voluntarily or upon questioning or noted on physical examination) from Olpasiran dosing through EOS are recorded/reported using the appropriate eCRF.

Serious treatment-emergent adverse events

The Investigator is responsible for ensuring that all serious TEAEs observed by the Investigator or reported by the subject that occur after signing of the ICF through 30 days after the dosing or the EOS visit (whichever is later) are reported using the appropriate eCRF and reported on the Serious Treatment-Emergent Adverse Event Report Form (described in [Appendix 1](#)).

All serious TEAEs will be collected, recorded, and reported to the Sponsor within 24 hours of the Investigator's knowledge of the event. The Investigator will submit any updated serious TEAE data to the Sponsor within 24 hours of it being available.

Serious Treatment-emergent Adverse Events after the Protocol-Required Reporting Period

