10. APPENDICES

Appendix 1. Safety Events: Definitions and Procedures for Recording, Evaluating, Follow-up, and Reporting of Treatment-emergent adverse event**Definition of Treatment-emergent adverse event**

Treatment-emergent adverse event Definition

• An adverse event is any untoward medical occurrence in a clinical study subject irrespective of a causal relationship with the study treatment.• Note: An adverse event can therefore be any unfavorable and unintended sign (including an abnormal laboratory finding), symptom, or disease (new or exacerbated) temporally associated with the use of a treatment, combination product, medical device, or procedure.• A treatment-emergent adverse event (TEAE) will be defined as an AE that starts during or after the first dose or starts prior to the first dose and increases in severity after the first dose.
Events Meeting the Treatment-emergent adverse event Definition

• Any abnormal laboratory test results (hematology, clinical chemistry, or urinalysis) or other safety assessments (e.g., electrocardiogram, radiological scans, vital signs measurements), including those that worsen from baseline, that are considered clinically significant in the medical and scientific judgment of the Investigator (i.e., not related to progression of underlying disease).• Exacerbation of a chronic or intermittent pre-existing condition including either an increase in frequency and/or intensity of the condition.• New conditions detected or diagnosed after study treatment administration even though it may have been present before the start of the study.• Signs, symptoms, or the clinical sequelae of a suspected drug-drug interaction.• Signs, symptoms, or the clinical sequelae of a suspected overdose of either study treatment or a concomitant medication. Overdose per se will not be reported as a TEAE/serious TEAE unless it is an intentional overdose taken with possible suicidal/self-harming intent. Such overdoses are to be reported regardless of sequelae.
Events NOT Meeting the Treatment-emergent adverse event Definition

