^f TEAEs will be recorded from initiation of study treatment on Day 1 until EOS/ET completion. Serious TEAEs will be recorded from the time the subject signs the Informed Consent Form until 30 days after the last dose of study treatment or the EOS (whichever is later).

^g Prior and concomitant medication administration will be recorded beginning at informed consent. Also, all Investigator-approved medications taken by a subject within 14 days or 5 half-lives (whichever is longer) before dosing on Day 1 for over-the-counter or prescription medications, and 30 days prior to Check-in for herbal medicines (e.g., St. John's wort), vitamins and dietary supplements (with the exception of those known to affect lipid metabolism, which are excluded), will be recorded on the subject's electronic Case Report Form.

^h Performed in serum at Screening and in urine at all other times for all females. A positive urine pregnancy test will be confirmed with a serum pregnancy test.

ⁱ Clinical chemistry (fasted at least 10 hours).

^j eGFR will be calculated using the Modification of Diet in Renal Disease (MDRD) equation.

^k Performed in postmenopausal females only.

^l Blood samples for determination of Olpasiran serum concentrations and PK parameters will be collected: Predose, 30 minutes, 60 minutes, 2, 3, 6, 9, 12, 24, and 36 hours postdose and on Study Days 3, 4, 7, 15, 29, 57, and 85 following administration of Olpasiran on Day 1. The PK samples collected on Day 1 will have a sampling window of \pm 10 minutes, postdose samples collected on Day 2 through Day 4 will have a sampling window of \pm 1 hour, postdose samples collected on Day 7 through Day 57 will have a sampling window of \pm 48 hours, and postdose samples collected on Day 85 through EOS will have a sampling window of \pm 5 days. Times of all PK samples will be recorded to the nearest minute.

^m Part 1 and Part 2 screening, and on study serum Lp(a) samples will be analyzed by a Sponsor-designated laboratory.

ⁿ At screening, lipids will measure triglycerides only. After screening, on-study lipids will include triglycerides, VLDL-C, LDL-C, HDL-C, total cholesterol, Apo A1, and total Apo B.

^o Subjects will be fasted overnight (at least 10 hours) before collection of blood samples for clinical chemistry evaluations or lipids.

Table 6. Schedule of Assessments

PROCEDURE	Treatment Period								EOS
	7	15	29	57	85	113	155	183	
Study Day	7	15	29	57	85	113	155	183	211 ^a
Study Time (Hours)	144								

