8.6. Safety and Tolerability Assessments

8.6.1. Adverse Events

All AEs will be coded using the Medical Dictionary for Regulatory Activities (MedDRA) Version 24.0 (or higher if upversioned during the study).

A treatment-emergent adverse event (TEAE) will be defined as any AE that starts on or after the first dose of investigational product (as determined by the flag indicating if the adverse event started prior to the first dose or not on the AE electric case report form) and up to EOS.

A treatment related TEAE will be defined as a TEAE with a relationship of possibly related or related to the study treatment, as determined by the investigator.

All AEs will be listed. In addition to the data recorded in the database, the listings will include derived onset time and duration. Onset time will be calculated from the time of dosing for TEAEs only.

The subject incidence of TEAE and the number of TEAEs will be summarized for the following categories based on safety analysis set:

- TEAEs (overall, serious, leading to study discontinuation, and leading to death) by treatment group
- TEAEs by severity and treatment group
- Treatment-related TEAEs (overall, serious, leading to study discontinuation, and leading to death) by treatment group
- Treatment-related TEAEs by severity and treatment group

The frequency of subjects will be summarized separately for TEAEs and treatment-related TEAEs events by the following:

- System organ class, preferred term, and treatment group
- Preferred term and treatment group

For the AE data the following rules will apply:

- For the derivation of TEAE status: If the start date/time of an AE is incomplete or missing, an AE will be assumed to be a TEAE, unless the incomplete start date/time or the end date/time indicates an AE started prior to the first dose.
- For the derivation of treatment-related TEAE status: If the study treatment relationship for a TEAE is missing, the treatment relationship will be kept as missing.

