10. SIGNIFICANT CHANGES FROM THE PROTOCOL-SPECIFIED ANALYSES

There were no significant changes from the protocol-specified analyses.

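### SAP 8.6.1 drops the protocol's worsening-after-dosing part of the TEAE definition without declaring it, so TEAE tables can omit such events

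*SAP*

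**What the plan says.** **Protocol, Appendix 1** gives the TEAE definition two limbs. An AE qualifies if it begins during or after the first dose, or if it "starts prior to the first dose and increases in severity after the first dose". The same appendix counts exacerbation of a pre-existing condition as a TEAE and leaves out ordinary fluctuation only where there is no worsening.

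**SAP, section 8.6.1** has one limb: "A treatment-emergent adverse event (TEAE) will be defined as any AE that starts on or after the first dose of investigational product", up to EOS. Status comes from the eCRF flag that records whether onset preceded the first dose. For missing or partial dates, an AE is presumed treatment-emergent "unless the incomplete start date/time or the end date/time indicates an AE started prior to the first dose". There is no exception for later worsening.

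**SAP, section 10** reads: "There were no significant changes from the protocol-specified analyses". SAP section 1 names section 10 as the place where significant changes are described.

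**Collection windows.** Protocol section 7.6.1 asks for non-serious TEAEs "from Olpasiran dosing through EOS are recorded/reported using the appropriate eCRF", and the footnotes to the Schedule of Assessments agree: "TEAEs will be recorded from initiation of study treatment on Day 1 until EOS/ET completion". Serious events are collected from consent, and on screening section 7.1.1 states: "The screening window is up to 40 days". The sample serious-event form has a box for events that precede the first dose.

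**The concern.** TEAEs are a secondary endpoint, and protocol section 8.5 specifies their tabulation by system organ class, preferred term and treatment group. The definition decides which events enter those tables. If the SAP's definition is narrower than the protocol's, the same data give two TEAE counts, and a reader of section 10 would believe that nothing had changed.

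The events at risk are those that were present before dosing and got worse after it. In a safety summary of a single-dose study, these are among the events that a treatment-emergent definition is meant to catch. Every AE summary in SAP 8.6.1 is restricted to TEAEs or treatment-related TEAEs, so an event that fails the definition is lost from the overall, serious, severity, relatedness and preferred-term tables together. It would stay in the listing of all AEs, but without a derived onset time, because the SAP derives onset time for TEAEs only.

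**Working it through.** **Step 1. The plan's own TEAE figure.** Protocol 8.1 and SAP 5 state about 90% confidence of seeing a TEAE in 8 subjects at 25% incidence, starting from 12 per group with 33.3% drop-out.

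- 12 × (1 − 0.333) = 8.0 subjects
- 1 − (1 − 0.25)^8 = 1 − 0.1001 = 0.8999

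The figure reproduces. It does not depend on which definition is used, and the documents give no share of TEAEs that arise only by worsening, so no revised figure is offered.

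**Step 2. The two definitions applied to the same records.**

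| Record | Protocol Appendix 1 | SAP 8.6.1 |
|---|---|---|
| Onset after dosing | TEAE | TEAE |
| Onset and end both before dosing | Not a TEAE | Not a TEAE |
| Onset before dosing, ongoing, no worsening | Not a TEAE | Not a TEAE |
| Worsening entered as a new record with postdose onset | TEAE | TEAE |
| One record with predose onset, worse after dosing | **TEAE** | **Not a TEAE** |

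Only the last row differs. Exacerbation of a medical-history condition entered with a postdose start falls in the fourth row and is not part of this finding.

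**Step 3. Can the last row occur?**

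- Serious events: yes. They are collected from consent, screening can last 40 days, and the report form provides for predose events.
- Non-serious events: less clear. Collection starts at dosing. However, an AE that begins at Check-in and worsens after dosing becomes a TEAE under Appendix 1 at a time inside the collection window, and the investigator must record its onset date. If the true predose onset is entered, the SAP flag excludes it.
- The documents do not say how a worsening predose AE is recorded. The Appendix 1 rule of one record at worst severity is worded for events that are already TEAEs. If it were applied here, the record would show a predose onset and the worst grade, with nothing to show when severity rose.

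**Step 4. Is it a version difference?** SAP section 1 cites a 2020 protocol. The protocol change logs, as far as they were available for this review, list no change to the TEAE definition, and the available SAP document history mentions none. A version difference does not appear to explain it. Parts of both logs were not available, so a note there cannot be ruled out.

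**Step 5. Size.** The safety set (SAP 7.2) keeps every dosed subject, so the denominator is 12 per group if all are dosed, and later drop-out does not change it. If k subjects in a group have a worsened predose AE and no other TEAE:

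fall in TEAE incidence = k/12

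| k (assumed) | Fall in group incidence |
|---|---|
| 0 | 0 points |
| 1 | 1/12 = 8.3 points |
| 2 | 2/12 = 16.7 points |

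The value of k is an assumption; neither document gives one.

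**The case against.** The best opposing case concedes the difference in wording and disputes its reach. On the clear route, a subject must have a serious AE that starts after consent, is still ongoing at dosing, does not prevent dosing, and then worsens. Eligibility works against this. Subjects must be in good health (protocol 4.1), a clinically significant disorder that the investigator judges a risk or an interference is excluded at Screening or Check-in, and the investigator may exclude anyone (4.2). Withdrawal before dosing is possible (4.5). Serious events in screen failures never reach the safety set. Much other worsening can be entered as a postdose event and would be counted. Two affected subjects in a group of 12 would be surprising. All AEs are listed, serious events reach the sponsor within 24 hours, and the study is small and descriptive. The authors might also regard a difference with almost no expected effect as not significant for section 10. Finally, the end-date part of the missing-date rule does no harm, since an event that ended before dosing cannot worsen afterwards.

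Most of this stands as an argument about size. The effect is probably small and may be zero, and the missing-date rule repeats the same narrowing and is not a separate defect. It does not remove the conflict. Followed as written, the SAP leaves a protocol-defined TEAE out of every AE summary table. Whether a worsening is entered as a new record depends on a recording convention that neither document states, so the tables cannot rely on it.

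**Conclusion.** The concern holds. SAP 8.6.1 omits the worsening limb of the protocol's TEAE definition, nothing else in that section restores it, and section 10 reports no change. The textual conflict is certain on the text available.

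The effect on counts is not certain. It can only be downward, at 8.3 points of group incidence per affected subject who has no other TEAE, and 0 to 16.7 points for an assumed 0 to 2 such subjects in a group of 12. The collection windows and entry criteria point to the low end. The PK primary endpoints are untouched. This should be fixed because a secondary endpoint is defined in two ways and the repair is cheap; no large bias is expected.

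**What to change.** 1. In SAP 8.6.1, state both limbs: onset during or after the first dose, or an AE that "starts prior to the first dose and increases in severity after the first dose", in each case up to EOS.
2. Extend the missing-date rule so that a predose start removes TEAE status only when no postdose increase in severity is recorded.
3. State how worsening is identified. One option is a separate AE record dated at the worsening, which the present SAP wording would already count. The other is a single record that holds the predose severity and the date of the increase.
4. Reconcile that choice with the single-record, worst-severity rule in protocol Appendix 1 and with the collection windows in protocol 7.6.1 and the Schedule of Assessments, under which predose severity is not collected for non-serious events.
5. If the narrower definition is intended, leave 8.6.1 as it is and declare and justify the difference in SAP section 10.

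**Cost.** Option 5 is about one sentence. Items 1 to 4 are a short SAP edit plus a recording rule or an extra date and severity field, and may need a protocol clarification. Reported TEAE incidence may be slightly higher. No change to dosing or clinical management is involved.

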8.6.2. Clinical Laboratory Parameters

All clinical laboratory parameters will be listed; any value outside the clinical reference range will be flagged. Separate listings will be provided for any parameter for which there is any individual subject value outside the respective clinical reference range.

Summary tables by timepoint along with change from baseline and percent change from baseline will be provided for clinical chemistry and hematology parameters based on safety analysis set. The baseline is defined as the last reading before dosing.

Values recorded as $<x$, $\leq x$, $>x$, or $\geq x$ will be displayed in the listings as recorded. For the derivation of listing flags and calculation of summary statistics, $<x$ and $\leq x$ values will be set to BLQ, whereas $>x$ and $\geq x$ values will be set to x.

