7.6.2 Clinical Laboratory Evaluations

Blood and urine samples will be collected for clinical laboratory evaluations (including coagulation panel, clinical chemistry, hematology, urinalysis, serology, and eGFR) at the times indicated in the Schedule of Assessments in [Appendix 9](#). Clinical laboratory evaluations are listed in [Appendix 2 Table 3](#). Blood will be collected after fasting at least 10 hours for clinical chemistry evaluations.

The Investigator is responsible for reviewing laboratory test results and recording any clinically relevant changes occurring during the study in CRF/eCRF. The Investigator must determine whether an abnormal value in an individual study subject represents a clinically significant change from the subject's baseline values. In general, abnormal laboratory findings without clinical significance (based on the Investigator's judgment) are not to be recorded as TEAEs. However, laboratory value changes that require treatment or adjustment in current therapy are considered TEAEs. Where applicable, clinical sequelae (not the laboratory abnormality) are to be recorded as the TEAE.

Subjects will be asked to provide urine samples for drugs of abuse screen and cotinine test, and will undergo an alcohol urine test at the times indicated in the Schedule of Assessments in [Appendix 9](#). For all female subjects, a pregnancy test and FSH screen for postmenopausal women will be performed at the times indicated in the Schedule of Assessments in [Appendix 9](#).

An Investigator (or designee) will perform a clinical assessment of all clinical laboratory data.

Pregnancy test

A highly sensitive serum pregnancy test should be completed at screening for all female subjects. A urine pregnancy test should be completed at all other times. A positive urine pregnancy test will be confirmed with a serum pregnancy test. A pregnancy test should be performed at the end of the study. (If a female subject, or the partner of a male subject, becomes pregnant it must be reported on the Pregnancy Notification Form, see [Figure 3](#)). Refer to [Appendix 4](#) for contraceptive requirements. Additional on-treatment pregnancy testing may be performed at the investigator' discretion or as required per local laws and regulations.

eGFR

eGFR will be calculated using the MDRD equation.

7.6.3 12-Lead Electrocardiogram

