8. SAMPLE SIZE AND DATA ANALYSIS

Data will be analyzed for all subjects who are randomized and receive Olpasiran. Descriptive statistics by treatment group will be provided for selected demographics, safety, PK and Lp(a) data. Descriptive statistics on continuous measurements will include means, medians, standard deviations, and ranges, while categorical data will be summarized using frequency counts and percentages. PK, Lp(a), lipids (as listed in [Table 4 in Appendix 2](#)), vital signs, ECG, and clinical laboratory data will be summarized at each scheduled visit per Schedule of Assessments.

Additional details will be included in the Statistical Analysis Plan (SAP).

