8.5 Safety Analysis

The final safety analysis for the study will be performed at the end of the study. No imputation will be done for safety assessments and endpoints for clinical laboratory tests, 12-lead ECGs, and vital signs will be summarized using descriptive statistics. Each TEAE will be coded using the Medical Dictionary for Regulatory Activities (MedDRA). Subject incidence of all TEAEs will be tabulated by system organ class and preferred term and by treatment group. Subject incidence tables of fatal TEAEs and serious TEAEs will be tabulated by treatment group. Subject-level data may be provided instead of tables if the subject incidence is low.

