8.5.4. Pharmacodynamic Statistical Methodology

Venous blood samples (approximately 6 mL) will be collected for measurement of Lp(a) at scheduled times.

Lipid panel will include triglycerides, very low-density lipoprotein cholesterol (VLDL-C), low-density lipoprotein cholesterol (LDL-C), and high-density lipoprotein cholesterol (HDL-C), total cholesterol, apolipoprotein A1 (ApoA1) and total apolipoprotein B (Apo B). At screening, lipid panel will measure triglycerides only. Venous blood samples (approximately 6 mL) will be collected for measurement of lipid panel at scheduled times. The lipid panel will be analyzed by a central lab of Covance Shanghai.

All PD parameters will be listed.

Summary tables and mean change and percent change from baseline (+ SE) figures by treatment and timepoint will be provided for all PD parameters based on PD analysis set.

Baseline is defined as the mean of last two non-missing values predose. If only 1 predose value is available then that value will be used as the baseline.

Values below the limit of quantification will be set to BLQ for the calculation of summary statistics.

Values recorded as $< x$, $\leq x$, $> x$, or $\geq x$ will be displayed in the listings as recorded. For the derivation of listing flags, calculation of summary statistics, and presentation in the figures, $< x$ and $\leq x$ values will be set to BLQ, whereas $> x$ and $\geq x$ values will be set to x .

No inferential statistical analyses are planned.

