8.6.3. Vital Signs Parameters

All vital signs parameters will be listed; any value outside the clinical reference range will be flagged.

Summary tables along with change from baseline and percent change from baseline will be provided for all vital signs parameters based on safety analysis set. The baseline is defined as the last reading before dosing.

8.6.4. 12-lead Electrocardiogram Parameters

All 12-lead ECG parameters will be listed; any value outside the clinical reference range will be flagged.

Summary tables by timepoint along with change from baseline and percent change from baseline will be provided for all 12-lead ECG parameters based on safety analysis set. The baseline is defined as the last reading before dosing.

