8.6.5. Other Assessments

All other safety and tolerability assessments not detailed in the above sections will be listed only.

Medical history will not be listed.

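### SAP 8.6.2 summarises only chemistry and hematology, so PT and APTT are listed but not tabulated, although the protocol promises by-visit summaries of clinical laboratory data

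*SAP*

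**What the plan says.** **Protocol.** Clinical laboratory tests are a secondary endpoint (section 2.2.2). Section 7.6.2 defines the scope as "clinical laboratory evaluations (including coagulation panel, clinical chemistry, hematology, urinalysis, serology, and eGFR". Table 3 in Appendix 2 gives the coagulation panel its own heading, with PT and APTT in it; INR is added only when hepatotoxicity is suspected. On analysis, section 8 says "vital signs, ECG, and clinical laboratory data will be summarized at each scheduled visit per Schedule of Assessments", and section 8.5 says "endpoints for clinical laboratory tests, 12-lead ECGs, and vital signs will be summarized using descriptive statistics".

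**SAP.** Section 8.6.2 puts every laboratory parameter into a listing, flags out-of-range values, and adds separate listings for any parameter with an out-of-range result. Its summary tables by timepoint are narrower: change and "percent change from baseline will be provided for clinical chemistry and hematology parameters based on safety analysis set". Section 8.6.5 adds a residual rule: "All other safety and tolerability assessments not detailed in the above sections will be listed only". No other section provides a coagulation summary. Section 10 states: "There were no significant changes from the protocol-specified analyses".

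**The concern.** The protocol's by-visit commitment covers clinical laboratory data without exception, and the protocol places coagulation within that term. The SAP drops it from the tables without giving a reason or declaring a change.

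Protocol section 1.5.2 names effects on platelets and coagulation as events of interest from other antisense therapies and includes coagulation among the safety assessments made during the study. Platelet count belongs to the hematology panel and will be summarised. PT and APTT will not.

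Listings keep each subject's values but do not describe the group's change from baseline, including shifts that stay inside the reference range. Exclusion criterion 3 adds to this. A subject whose screening PT or APTT is out of range may still enrol if the result is judged not clinically significant. For such a subject an out-of-range flag may already be present before dosing, so the flag alone does not separate baseline status from postdose change.

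**Working it through.** This is mainly a comparison of texts, followed by a count of the data affected.

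**1. Is coagulation part of clinical laboratory data?** Yes. Section 7.6.2 names it in the definition.

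**2. Could hematology in the SAP be read to include it?** Not in these documents. The two are separate entries in section 7.6.2, Table 3, the blood-volume table (Appendix 3) and both schedule tables (Appendix 9).

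**3. Do the other SAP sections narrow their scope in the same way?** No. For vital signs, section 8.6.3 says "percent change from baseline will be provided for all vital signs parameters based on safety analysis set". Section 8.6.4 has the same scope for ECG. For pharmacodynamics, section 8.5.4 says the tables and figures "will be provided for all PD parameters based on PD analysis set". Of these sections, only the laboratory one is cut down to named categories.

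**4. How much data is affected?** Inputs: Appendix 3 (maximum draws per subject), Tables 5 and 6 (timing), and the sample-size section (24 subjects, 33.3% drop-out).

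| Panel | Draws, Appendix 3 | Predose | Postdose, Table 5 | Postdose, Table 6 | Postdose total |
|---|---|---|---|---|---|
| Coagulation | 9 | 2 | 2 | 5 | 7 |
| Chemistry and hematology | 12 | 2 | 2 | 8 | 10 |

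The schedule reproduces the Appendix 3 counts: 2 + 2 + 5 = 9 and 2 + 2 + 8 = 12. The coagulation volume also agrees: 9 × 3 mL = 27 mL.

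- Postdose coagulation panels, everyone completing: 7 × 24 = 168.
- The plan's drop-out assumption leaves 12 × (1 − 1/3) = 8 per group, or 16 in all. If the 8 drop-outs gave no postdose sample: 7 × 16 = 112.
- The two Table 5 draws fall within in-house residency. If every drop-out gave those two: 112 + 2 × 8 = 128.
- Postdose chemistry and hematology panels: 10 × 24 = 240.

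Under the SAP text, none of the 112 to 168 coagulation panels reaches a summary table.

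**5. Other panels.** Urinalysis has 1 + 2 = 3 postdose samples per subject and is in the same position. Serology, FSH and eGFR are done at screening only, so a by-visit summary does not apply to them.

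**The case against.** - **Latitude in the protocol.** The sentence in section 8 on summaries by treatment group covers only selected safety data, and details are deferred to the SAP. This stands for the grouping. It does not reach the next commitment, on summaries by visit, which is unrestricted. SAP section 6 supplies the grouping for safety summaries.
- **Unseen table shells.** SAP section 1 places the detailed table descriptions in a separate shells document, and the SAP's document history shows that shells were edited during the study. A coagulation table may exist there. This stands, and it limits the finding to the SAP text: whether the clinical study report would lack the table cannot be established from these documents.
- **Section 10 covers significant changes only.** Leaving out one table may not count as significant, and SAP section 1 allows modifications agreed with the sponsor. That is fair. The weight falls on the mismatch between SAP 8.6.2 and the protocol, not on section 10 being false.
- **Section 8.6.5 adds little.** Section 8.6.2 already leaves coagulation in listings, so the residual rule is not needed to reach the conclusion.
- **Listings are enough in 24 subjects.** All values remain visible, an out-of-range PT or APTT gets its own listing, and clinically significant changes are reportable as TEAEs. This limits the harm. It does not supply the descriptive summary that the protocol promises.
- **Sample counts are not effects.** True. They show how much data goes unsummarised, not a change in any result.

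**Conclusion.** The concern holds, as a minor one. As written, the SAP gives PT and APTT no summary by group and timepoint, while protocol sections 8 and 8.5 commit to summarising clinical laboratory data. Up to 7 postdose panels per subject are affected, at most 168 in all.

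No primary endpoint or inference depends on this, and no individual data are lost. The protocol says that the class risks have not been borne out for olpasiran. With no control arm, a group shift in PT or APTT could not by itself be attributed to the drug.

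The conclusion rests on two things: the SAP text governs where the shells cannot be seen, and the protocol's separate naming of the coagulation panel carries over to the SAP.

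**What to change.** In SAP 8.6.2, extend the summary tables from clinical chemistry and hematology to clinical chemistry, hematology and coagulation (PT, APTT), showing value, change and percent change from baseline by timepoint and treatment group. Align the table shells. In SAP section 10, state that urinalysis and the screening-only tests will be listed only.

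If the shells already contain a coagulation table, only the SAP text needs to change. Declaring in section 10, with a reason, that PT and APTT are listed only would remove the inconsistency but would not restore the promised summary.

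The cost is one phrase, one sentence, and at most one more run of a table program already planned for chemistry and hematology. The samples are already in the schedule, so no new data are needed.
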